## 9. STATISTICAL CONSIDERATIONS AND DATA ANALYSES

### 9.1. Hypotheses

The primary objective of the study is to investigate the safety and tolerability of GSK2982772 following 12 weeks of treatment. No formal statistical hypotheses will be conducted to assess this objective.

If appropriate, comparisons between the GSK2982772 and the placebo arm will be made to investigate the secondary pharmacodynamic, mechanistic and efficacy objectives.

Trends over time will be investigated for both treatment arms along with associations between each of the pharmacodynamic, mechanistic and efficacy parameters.

### 9.2. Sample Size Considerations

[figure not shown]
#### 9.2.1. Sample Size Assumptions

The study is not powered to detect pre-defined differences. A sufficient number of subjects will be screened so that approximately 24 subjects with moderate to severe RA are randomised into the study on a TID regimen. Prior to protocol amendment 3 being approved in each country, no more than 18 subjects will be randomised into the study on a BID regimen. [Table 4](#) summarises the total planned sample sizes for BID and TID regimens. Should the drop-out rate be higher than anticipated, additional or replacement subjects may be randomised (up to an overall total maximum of 48) into the study at the discretion of the Sponsor.

**Table 4 Summary of Total Sample Size by Dosing Regimen**

Number Randomised to GSK2982772 60 mg BID or Placebo BID	Number Randomised to GSK2982772 60 mg TID or Placebo TID	Revised Max Total Sample Size	Total + Additional/ Replacement Subjects
7 - 12	24	36	42
12 - 18	24	42	48

The primary objective of the study is safety and tolerability, where there will be 20 subjects randomised to GSK2982772 60 mg TID and up to 12 subjects randomised to GSK2982772 60 mg BID. Using a Bayesian approach to determine the confidence interval (CI) around an observed safety event, we would assume a flat Beta (1, 1) prior, and if we were to observe one safety event in 16 then the posterior distribution would be Beta (2, 16), as outlined below in [Figure 4](#).

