### 6.2. Treatment Assignment

At Screening a unique Subject Number will be assigned to any subject who has signed a consent form. The unique Subject Number will be used to identify individual subjects during the course of the study. Any subject that is re-screened outside of the allowed screening window at the approval of the GSK Medical Monitor, must be assigned a new unique Subject Number.

Subjects who meet screening eligibility criteria will be randomised to a treatment group through an Interactive Response Technology System (IRTS). The IRTS will confirm the subject’s CRF number (Subject Number) and provide the randomisation number, where:

- A randomisation number will be assigned from a randomisation schedule generated by Clinical Statistics, prior to the start of the study, using validated internal software. Once assigned, this number must not be reassigned to any other subject in the study.

Therefore, the randomisation is centrally controlled by the IRTS.

Subjects will be randomised to receive either GSK2982772 or placebo in a 2:1 ratio.

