**Figure 4 One Event in 16 Subjects: Beta (2,16) Distribution**

Thus, we can be 95% certain that the true probability of the safety event lies between 2% and 25%.

For supportive information, the properties of the key secondary endpoint DAS28 have been considered.

Based on the estimate of variability (SD=1 from historical data) it is estimated that the lower and upper bounds of the 95% CI for the change from baseline in DAS28-CRP score will be within approximately 0.693 and 0.490 of the point estimate of GSK2982772 60 mg TID (n=16) and placebo (n=8).

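### Section 9.2.1 states 20 active TID subjects where the design gives 16 and, as a separate error, labels a 90% credible interval for the safety event rate as 95%

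*Protocol*

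**What the plan says.** Section 9.2.1 plans that "approximately 24 subjects with moderate to severe RA are randomised into the study on a TID regimen", and Section 6.2 sets the allocation: "Subjects will be randomised to receive either GSK2982772 or placebo in a 2:1 ratio". For the period before Amendment 3, Section 9.2.1 adds that "no more than 18 subjects will be randomised into the study on a BID regimen".

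The text under Table 4 then gives the numbers on active drug: "there will be 20 subjects randomised to GSK2982772 60 mg TID and up to 12 subjects randomised to GSK2982772 60 mg BID". The same paragraph illustrates the precision available for safety: "we would assume a flat Beta (1, 1) prior", one event is observed among 16 subjects, and the posterior is Beta(2,16). After Figure 4 the text concludes that "we can be 95% certain that the true probability of the safety event lies between 2% and 25"%.

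The DAS28-CRP precision statement that follows uses 16 active TID and 8 placebo subjects. Section 9.2.2 takes 16 as its reference number. Table 5, headed as upper limits of exact 95% credible intervals, gives 28.7% for 16 subjects and one event.

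**The concern.** Neither figure fits the rest of the section. An active TID arm of 20 cannot come from 24 subjects at 2:1. An upper limit of 25% at the 95% level cannot stand beside 28.7% in Table 5 for the same data, prior and stated level.

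Safety and tolerability is the primary objective. Section 9.1 tests no formal hypothesis for it, and Section 9.2.1 says the study is not powered. Numbers exposed and interval width are therefore what the sample size rests on. Someone reading only Section 9.2.1 would take the exposed group to be larger than planned, and would believe that after one event in 16 a true rate between 25% and 28.7% had been excluded with 95% certainty.

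**Working it through.** **Inputs.** TID total 24 and BID maximum 18 (Section 9.2.1); allocation 2:1 (Section 6.2); prior Beta(1,1), one event in 16, posterior Beta(2,16) (text under Table 4); printed interval 2% to 25% at 95% (text after Figure 4); Table 5 limits (Section 9.2.2).

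**Arm size.**
- TID active: 24 × 2/3 = 16; placebo 24 × 1/3 = 8.
- BID active: 18 × 2/3 = 12, so the BID half of the sentence is right.
- Cross-check with SD = 1: the half-width 1.96/√n is 1.96/√16 = 0.490 and 1.96/√8 = 0.693. These are the two DAS28-CRP values printed (listed in the opposite order to the arms), so that calculation assumed a 16:8 split.
- The sentence overstates the active TID arm by 20 − 16 = 4 subjects.

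**Interval.** The Beta(2,16) distribution function has a closed form, F(p) = 1 − (1 − p)^16 × (1 + 16p).

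Testing the printed limits first:
- Above 25%: 0.75^16 × (1 + 4) = 0.01002 × 5 = 0.050.
- Below 2%: 1 − 0.98^16 × 1.32 = 1 − 0.9554 = 0.045.
- Inside 2% to 25%: 1 − 0.050 − 0.045 = 0.905.

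The printed range therefore holds about 90%, with close to 5% in each tail. Posterior quantiles confirm this:

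| Interval for one event in 16 | Lower | Upper |
|---|---|---|
| Printed, called 95% | 2% | 25% |
| 90% equal-tailed, Beta(2,16) | 2.13% | 25.01% |
| 95% equal-tailed, Beta(2,16) | 1.46% | 28.69% |
| 95% highest-density, Beta(2,16) | 0.34% | 25.18% |
| 95% Jeffreys prior | 0.7% | 25.7% |
| 95% Clopper-Pearson | 0.2% | 30.2% |
| 95% Wilson | 1.1% | 28.3% |
| 95% Wald | −5.6% | 18.1% |

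No 95% method tried gives both 2% and 25%. Rounding does not explain it either: the content of the widest range that rounds to 2% and 25% (1.5% to 25.5%) is 0.928.

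**Table 5.** All 15 entries reproduce as the 97.5% quantile of Beta(1 + x, 1 + n − x), the upper end of a 95% equal-tailed interval. For n = 16 they are 19.5%, 28.7% and 36.4% for zero, one and two events; for n = 20 they are 16.1%, 23.8% and 30.4%. Table 5 is correct and shows which convention the section intends.

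**The case against.** **Replacement subjects.** Table 4 allows six additional or replacement subjects. If all six joined the TID cohort, 30 × 2/3 = 20. But those subjects are at the sponsor's discretion and depend on drop-out, whereas the sentence is unconditional. It also pairs 20 with a BID figure of 12 = 18 × 2/3 that includes no replacements. This reading fails.

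**Drop-out.** Since Section 9.2.2 speaks of completers, 20 could be the number randomised and 16 the number completing. Twenty active subjects at 2:1 still need 30 randomised, against a plan of about 24, and the 16:8 split already uses all 24. The word 'approximately' does not stretch that far.

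**One-sided reading.** The posterior probability of a rate below 25% is 0.950, so 25% is a valid one-sided 95% upper bound. The sentence, however, gives two limits and claims 95% for the range between them.

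**Consequences.** This part of the objection stands. The correct limit for the same case is printed in Table 5, so a careful reader sees two inconsistent figures, one of them right. Section 9.4.1 bases the primary analysis on clinical review of displays. The stopping criteria do not use the interval, and the number to be randomised is set by 24 and the 2:1 ratio. Both slips look editorial: the amendment log shows the target moving from 30 to 24, and 30 × 2/3 = 20.

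**Conclusion.** Both errors are in the current text and both favour the design, but they are separate.

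- **Arm size:** 20 stated, 16 correct.
- **Interval:** 2% to 25% stated as 95%; its actual content is 90.5%. The 95% equal-tailed interval is 1.5% to 28.7%, so the upper limit is understated by 28.7 − 25 = 3.7 percentage points. The difference at the lower limit is trivial.

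A reader might infer that the wrong arm size is what makes the interval too narrow. The documents do not support that: the printed posterior already uses 16, and only the mislabelled level affects the limits. A reader might also infer that the protocol has no correct planning figures for safety, or that the safety assessment is compromised. Neither follows, because Table 5 is correct and no analysis, stopping criterion or decision rule depends on either number. Severity is moderate to minor.

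The conclusion assumes that the intended interval is equal-tailed, as Table 5 is throughout, and that 24 and 2:1 are the operative design figures. Section 9 of the Germany-specific Amendment 4 is not in the text available, so whether the wording persists there could not be checked.

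**What to change.** In Section 9.2.1:

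1. Change the number randomised to GSK2982772 60 mg TID from 20 to 16. The BID figure of up to 12 stays.
2. Replace 2% and 25% by 1.5% and 28.7%, keeping the 95% label. Keeping 2% to 25% and calling it 90% would be equally accurate, but the first option matches Table 5 and is preferable.

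Table 5 needs no change. If the same sentences appear in Amendment 4, correct them there too. The cost is a text correction at the next amendment: no extra subjects and no change to design or analysis. The stated precision becomes slightly less favourable.

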**Figure 4 One Event in 16 Subjects: Beta (2,16) Distribution**

Thus, we can be 95% certain that the true probability of the safety event lies between 2% and 25%.

For supportive information, the properties of the key secondary endpoint DAS28 have been considered.

Based on the estimate of variability (SD=1 from historical data) it is estimated that the lower and upper bounds of the 95% CI for the change from baseline in DAS28-CRP score will be within approximately 0.693 and 0.490 of the point estimate of GSK2982772 60 mg TID (n=16) and placebo (n=8).

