## **Analysis**

The safety and tolerability of GSK2982772 following 12 weeks of treatment will be based on the review and displays of adverse events, clinical laboratory values, vital sign measurements and 12-lead electrocardiogram (ECG) monitoring.

Ongoing reviews of available efficacy, pharmacodynamic and mechanistic endpoints will be conducted during the study by a Data Review Committee (DRC), consisting of a limited number of GlaxoSmithKline (GSK) individuals, some of who are also members of the GSK study team who are not involved with the day-to-day running of the study. The primary purpose of these reviews will be to monitor target engagement, inflammatory markers and Disease activity score for 28 different joints with (CRP) value (DAS28-CRP) for futility and internal decision making. A data review charter will outline in detail the activities of this review and how the integrity of the study will be maintained.

A formal interim analysis will be conducted during the study, when an appropriate number of subjects have completed 12 weeks of treatment or on the request of the DRC. The purpose of this interim will be to assess whether to stop the study for futility. This interim analysis may also facilitate decision making regarding the subsequent clinical development of GSK2982772 for RA.

Comparisons between treatment groups on any changes observed will be conducted for the secondary endpoints if deemed appropriate, e.g. changes in the mean target engagement, changes in inflammatory markers and percentage change in DAS28-CRP

will be statistically analysed using a Mixed-effect Model Repeat Measurements (MMRM) comparing GSK2982772 with placebo at each time point.

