##### **9.4.2. Secondary Analyses**

The relationship between each of the mechanistic endpoints and also with the clinical endpoints will be graphically presented and analysed using an appropriate statistical model identifying any trends. The model will determine whether the mechanistic effect significantly explains or predicts the effect on the other mechanistic or clinical endpoints (e.g., DAS28-CRP score). This may be conducted through comparing statistical models incorporating different explanatory terms (i.e. mechanistic endpoints) with the 'null' model (no mechanistic endpoints); or if deemed appropriate, multivariate statistical methods may also be applied to determine the relationship between the key endpoints. The consistency in the changes over time between the endpoints will also be assessed.

Each endpoint will be considered individually and at the treatment level, where comparisons between treatment groups would be made on any changes observed, if deemed appropriate. This could include change from baseline in DAS28-CRP, which will be statistically analysed using a MMRM analysis comparing GSK2982772 with placebo

at each time point. Additionally this could include, the proportion of subjects achieving ACR20/50/70 and DAS28-CRP response, which will be statistically analysed using a Generalised Estimating Equation (GEE) model comparing GSK2982772 with placebo at each timepoint. Similar analyses will be conducted for other secondary endpoints if deemed appropriate.

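### Section 9.2.1 attaches the DAS28-CRP half-widths to the wrong arms, and the synopsis names percentage change where the rest of the protocol uses change from baseline

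*Protocol*

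**What the plan says.** Section 9.2.1 states that "The study is not powered to detect pre-defined differences" and then, as supportive information, describes the precision expected for DAS28, which it calls the key secondary endpoint. The input is given as "Based on the estimate of variability (SD=1 from historical data"). The quantity described is "the lower and upper bounds of the 95% CI for the change from baseline in DAS28-CRP score", and the bounds are said to be "within approximately 0.693 and 0.490 of the point estimate of GSK2982772 60 mg TID (n=16) and placebo (n=8").

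The outcome scale appears in several places. The endpoint tables in the synopsis and in Section 3 list change from baseline in DAS28-CRP. Section 9.4.2 agrees: "This could include change from baseline in DAS28-CRP, which will be statistically analysed using a MMRM analysis comparing GSK2982772 with placebo". The Analysis part of the synopsis does not. Its examples for the mixed model include "changes in inflammatory markers and percentage change in DAS28-CRP". That phrase stands in both the Amendment 3 and the Amendment 4 text of the synopsis.

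**The concern.** If both arms share one SD, the arm with twice as many subjects must have the narrower interval. The printed order gives it the wider one. Someone using Section 9.2.1 to judge how well each arm mean will be estimated would be too pessimistic about active and too optimistic about placebo. Placebo is the small comparator arm, and Section 9.3.2 makes DAS28-CRP the main subject of the unblinded futility reviews.

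The scale matters for a different reason. An SD of 1 is in DAS28 points. Percentage change divides each subject's change by that subject's own baseline, so it is a different outcome with a different SD, and it weights subjects differently. With both scales in the protocol, either could be cited as the planned one.

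**Working it through.** **Inputs, all from the protocol**
- SD of change from baseline: 1, in both arms (Section 9.2.1).
- Confidence level: 95%, two-sided (Section 9.2.1).
- Arm sizes: 16 and 8, printed in the sentence itself. They follow from "approximately 24 subjects with moderate to severe RA are randomised into the study on a TID regimen" (Section 9.2.1) and "Subjects will be randomised to receive either GSK2982772 or placebo in a 2:1 ratio" (Section 6.2): 24 × 2/3 = 16 and 24 × 1/3 = 8.

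**Reproducing the printed figures**

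Half-width = 1.96 × SD/√n.
- GSK2982772, n=16: 1.96 × 1/4 = 0.490.
- Placebo, n=8: 1.96 × 1/2.828 = 0.693.

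Both printed numbers come back to three decimals, but only with the arms exchanged. So the normal quantile was evidently used and the labels are transposed.

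**Can the printed order be rescued?**
- t quantile, n−1 df: 2.131/4 = 0.533 (n=16) and 2.365/2.828 = 0.836 (n=8). No.
- t quantile, 22 df: 2.074/4 = 0.518 and 2.074/2.828 = 0.733. No.
- One-sided 95% normal quantile: 0.411 (n=16) and 0.582 (n=8). No.
- Difference between arms: 1.96 × √(1/16 + 1/8) = 0.849, or 0.898 with t on 22 df. Neither is printed.
- Unequal SDs: the printed order would need SD = 0.693 × 4/1.96 = 1.41 on active and 0.490 × 2.828/1.96 = 0.71 on placebo. The protocol gives one SD of 1.
- Section 9.2.1 also speaks of 20 subjects on active TID. With n=20 the normal half-width is 0.438, which is not printed either.

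**Size of the transposition**
- Active: 0.693/0.490 = 1.41, so 41% too wide as printed.
- Placebo: 0.490/0.693 = 0.71, so 29% too narrow as printed.

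**The scale, place by place**
- Synopsis endpoint table: change from baseline.
- Section 3 endpoint table: change from baseline.
- Section 9.2.1 precision statement: change from baseline.
- Section 9.4.2 mixed model: change from baseline.
- Synopsis Analysis text: percentage change.

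Percentage change = 100 × change/baseline. Turning an SD of 1 point into an SD in percent needs the baseline distribution and its correlation with change. The protocol gives neither, so the precision statement cannot be carried over to the synopsis scale.

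**The case against.** The sentence lacks the word 'respectively', is qualified as approximate and is offered only as support in a study without power requirements. Both numbers are right for an SD of 1, and a statistician would see at once which belongs to which arm. The sample size does not rest on them, Section 9.2.3 rules out re-estimation, and the futility text in Section 9.3.2 uses neither. The percentage-change phrase is one example under a conditional, against four places that agree with each other. All of this stands and limits the consequence. It does not make the printed order right or reconcile the two scales.

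Three stronger readings are tempting, and the documents do not support them.

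First, a reader might infer that the normal quantile is itself an error and that even the correctly placed placebo figure is 17% too narrow (0.693 against 0.836). But the SD is a fixed planning value from historical data, and a normal quantile with a known SD is an accepted convention. The 17% also assumes the placebo variance is estimated from 8 subjects alone. With one SD pooled over both arms (22 df), the normal figures are about 5.5% narrower than the t figures throughout (1.960/2.074 = 0.945).

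Second, a reader might count the missing precision of the between-arm difference as an error. The protocol does not promise it, and the treatment comparison is itself conditional.

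Third, a reader might conclude that the wrong scale will be analysed. The endpoint tables and Section 9.4.2 point clearly to change from baseline; the synopsis phrase is the outlier.

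**Conclusion.** Two statements are wrong as written. The DAS28-CRP half-widths in Section 9.2.1 are transposed: with SD=1 treated as known and a two-sided 95% normal interval, they should be about 0.490 for GSK2982772 60 mg TID (n=16) and about 0.693 for placebo (n=8). The Analysis text of the synopsis contradicts the rest of the protocol on the outcome scale. The first conclusion rests only on the common SD and the arm sizes that the protocol states; the second rests on comparing its own sections. No design choice, sample size or stated decision rule changes. The case for correcting them is that they describe the precision and the scale of the endpoint the protocol names as its key secondary one.

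**What to change.** In Section 9.2.1, restate the half-widths as approximately 0.490 for GSK2982772 60 mg TID (n=16) and 0.693 for placebo (n=8), respectively, treating SD=1 as known.

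In the Analysis part of the synopsis, in both amendment texts, replace percentage change in DAS28-CRP with change from baseline in DAS28-CRP.

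Optionally, add what to expect when the SD is estimated, on one consistent basis: with an SD of 1 pooled over both arms on 22 df, the half-widths are about 0.52 (active), 0.73 (placebo) and 0.90 (difference). Arm intervals that use separate variances should not be set beside a pooled-variance difference.

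The cost is one sentence and one phrase, with no change to design, conduct or sample size.

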### 9.2.2. Sample Size Sensitivity

A sample size sensitivity analysis has been conducted on the primary endpoint to investigate the different safety event rates. If the number of subjects who complete the 12 weeks is higher or lower than 16 in the GSK2982772 group, then the true incidence rates of safety events that could not be ruled out (as outlined in Section 9.2.1) would change. These changes are outlined in Table 5.

**Table 5 Sample Size Sensitivity**

GSK2982772 subjects completing the study	Number of a particular safety event observed with GSK2982772	Upper limit of exact 95% Credible Interval indicating that a true incidence rate of x% could not be ruled out
20	0	16.1%
20	1	23.8%
20	2	30.4%
18	0	17.6%
18	1	26.0%
18	2	33.1%
16	0	19.5%

GSK2982772 subjects completing the study	Number of a particular safety event observed with GSK2982772	Upper limit of exact 95% Credible Interval indicating that a true incidence rate of x% could not be ruled out
16	1	28.7%
16	2	36.4%
14	0	21.8%
14	1	31.9%
14	2	40.5%
12	0	24.7%
12	1	36.0%
12	2	45.4%

### 9.2.3. Sample Size Re-estimation or Adjustment

No sample size re-estimation or adjustment will be conducted.

## 9.3. Data Analysis Considerations

### 9.3.1. Analysis Populations

**All Subjects Population:** The ‘All Subjects Population’ is defined as subjects who were screened for the study. This population is used for the summary of selected accountability data.

**Safety Population:** The ‘Safety Population’ is defined as subjects who receive at least one dose of study medication. This population is used for the summary of all data including demography, safety, efficacy and exploratory data but excluding PK data.

**Pharmacokinetic Population:** The ‘PK Population’ is defined as subjects in the ‘Safety’ population who received an active dose and for whom a GSK2982772 pharmacokinetic sample was obtained and analysed. This population is used for the summary of PK data only. Any PK-PD analysis will be conducted on the Safety population such that subjects receiving placebo can be included.

If 12 or more subjects are randomised to a BID regimen (i.e.,  $\geq 4$  placebo and  $\geq 8$  GSK2982772 60 mg BID) then treatment received will take into account dosing frequency for GSK2982772, otherwise treatment will be irrespective of dosing frequency.

